APPENDIX F: STUDY SCHEMA

Identify, Screen, & Recruit Participants

- RA uses study-specific Epic Workbench report to identify potentially eligible patients that are either (1) approaching first transfusion or (2) transfusion-dependent
- RA approaches 75 potentially eligible patients over the course of 15 months (23 at YCC and WFB, 29 at DFCI; goal is to reach 60 completed peri-transfusion quality of life assessments [PTQAs])
- Patients approached for consent discussion at appointment prior to first/next transfusion
- Willing participants consented to study and given study packet, including the QUALMS survey

Peri-Transfusion Quality of Life Assessment (PTQA)

Pre-Transfusion QOL Survey Administration

- RA calls participants with reminder to complete survey on the day prior to transfusion
- Participants fill out QUALMS survey at home on day prior to first/next pRBC transfusion

Post-Transfusion QOL Survey Administration

- On the day of transfusion, consenting participants given a second paper copy of the QUALMS survey with a stamped envelope addressed to appropriate site
- RA calls participants with reminder to complete survey exactly one week post-transfusion
- Participants fill out survey at home exactly one week post-transfusion; asked to mail survey back

Dissemination of PTQA Report

- Once received, second QUALMS survey scored and compared with the first
 - Stable QOL = post-transfusion score within 5 points of pre-transfusion score
 - Improved QOL = post-transfusion score 5 or more points higher than pre-transfusion score
 - Worsened QOL = post-transfusion score 5 or more points lower than pre-transfusion score
- Both patient and provider sent a report with PTQA results
 - Report will include language encouraging patients/providers to use results to inform next transfusion decision
 - Report will specifically suggest future transfusions be halted or decreased in frequency if QOL did not improve

Data Analysis

- Participants compared with historical controls (matched for transfusion group; pre-transfusion Hb; IPSS-R; and institution) seen between 2015 and 2017
 - For newly transfused, primary outcome is receipt of second transfusion (yes/no) within two months after index transfusion
 - For transfusion-dependent, primary outcome is number of units pRBCs received within two months after index transfusion
 - At two months post-transfusion, we will compare number of hospitalizations and clinic visits with number before index transfusion
- At two months post-transfusion, we will also send participants a follow-up survey to assess secondary outcomes, including PTQA utilization, decisional regret, perceptions of care, and perceived stress

PROTOCOL TITLE: A New Paradigm of Transfusion Decision Support for Patients with MDS:

Using Peri-Transfusion Quality of Life Assessments (PTQAs)

APPENDIX G: QUESTIONNAIRE REMINDER CALL

PRE-TRANSFUSION

Hello - may I please speak to [PATIENT NAME]?

My name is [RESEARCH ASSISTANT], and I am calling from Dr. [NAME OF PROVIDER] office regarding the quality of life study you signed up for at your last appointment. This is a reminder to fill out your pre-transfusion study survey today. Please bring it with you to your upcoming transfusion appointment. I will meet you during your appointment to collect your completed survey and give you a second questionnaire for you to fill out one week after your appointment. Do you have any questions for me today?

Great! I'm looking forward to seeing you at your appointment. Thank you!

POST-TRANSFUSION

Hello - may I please speak to [PATIENT NAME]?

My name is [RESEARCH ASSISTANT], and I am calling from Dr. [NAME OF PROVIDER] office regarding the quality of life study. This is a reminder to fill out your post-transfusion study survey today. Once you've completed it, please send it back to us using the pre-stamped, pre-addressed envelope I gave you at your last appointment. Once we receive the completed survey, we will compare the results from your pre- and post-transfusion surveys and send you and your doctor a report with the results. Do you have any questions for me today?

30.0 Great! I'm looking forward to seeing you at your appointment. Thank you!

**PROTOCOL TITLE: A New Paradigm of Transfusion Decision Support for Patients with MDS:
Using Peri-Transfusion Quality of Life Assessments (PTQAs)**

APPENDIX H: DSMP

INTRODUCTION

The Dana-Farber/Harvard Cancer Center Multi-Center Data and Safety Monitoring Plan (DF/HCC DSMP) outlines the procedures for conducting a DF/HCC Multi-Center research protocol. The DF/HCC DSMP serves as a reference for any sites external to DF/HCC that are participating in a DF/HCC clinical trial.

Purpose

To establish standards that will ensure that a Dana-Farber/Harvard Cancer Center Multi-Center protocol will comply with Federal Regulations, Health Insurance Portability and Accountability Act (HIPAA) requirements and applicable DF/HCC Standard Operating Procedures.

Multi-Center Data and Safety Monitoring Plan Definitions

DF/HCC Multi-Center Protocol: A research protocol in which one or more outside institutions are collaborating with Dana-Farber/Harvard Cancer Center where a DF/HCC investigator is the sponsor. DF/HCC includes Dana-Farber/Partners Cancer Care (DF/PCC) Network Clinical Trial Affiliates.

Lead Institution: One of the Dana-Farber/Harvard Cancer Center consortium members (Dana-Farber Cancer Institute (DFCI), Massachusetts General Hospital (MGH), Beth Israel Deaconess Medical Center (BIDMC), Boston Children's Hospital (BCH), Brigham and Women's Hospital (BWH) responsible for the coordination, development, submission, and approval of a protocol as well as its subsequent amendments per the DFCI IRB and applicable regulatory guidelines (CTEP, Food and Drug Administration (FDA), Office of Biotechnology Activities (OBA) etc.). The Lead Institution is typically the home of the DF/HCC Sponsor. The Lead Institution also typically serves as the Coordinating Center for the DF/HCC Multi-Center Protocol.

DF/HCC Sponsor: The person sponsoring the submitted Multi-Center protocol who takes responsibility for initiation, management and conduct of the protocol at all research locations. In applicable protocols, the DF/HCC Sponsor will serve as the single liaison with any regulatory agencies. The DF/HCC Sponsor has ultimate authority over the protocol and is responsible for the conduct of the study at DF/HCC and all Participating Institutions. In most cases the DF/HCC Sponsor is the same person as the DF/HCC Overall Principal Investigator; however, both roles can be filled by two different people.

Participating Institution: An institution that is outside the DF/HCC and DF/PCC consortium that is collaborating with DF/HCC on a protocol where the sponsor is a DF/HCC Investigator. The Participating Institution acknowledges the DF/HCC Sponsor as having the ultimate authority and responsibility for the overall conduct of the study.

Coordinating Center: The entity (i.e. Lead Institution, Medical Monitor, Contract Research Organization (CRO), etc) that provides administrative support to the DF/HCC Sponsor in order that he/she may fulfill the responsibilities outlined in the protocol document and DSMP, and as specified

**PROTOCOL TITLE: A New Paradigm of Transfusion Decision Support for Patients with MDS:
Using Peri-Transfusion Quality of Life Assessments (PTQAs)**

in applicable regulatory guidelines (i.e. CTEP Multi-Center Guidelines). In general, the Lead Institution is the Coordinating Center for the DF/HCC Multi-Center Protocol.

DF/HCC Office of Data Quality (ODQ): A group within DF/HCC responsible ensuring high-quality standards are used for data collection and the ongoing management of clinical trials, auditing, and data and safety monitoring. ODQ also coordinates quality assurance efforts related to multi-center clinical research.

DF/HCC Clinical Trials Research Informatics Office (CTRIO): A group within DF/HCC responsible for providing a comprehensive data management platform for managing clinical trial data.

GENERAL ROLES AND RESPONSIBILITIES

For DF/HCC Multi-Center Protocols, the DF/HCC Sponsor, the Coordinating Center, and the Participating Institutions (Yale Cancer Center and Wake Forest Baptist) are expected to adhere to the following general responsibilities:

DF/HCC Sponsor

The DF/HCC Sponsor, [name], MPH, will accept responsibility for all aspects of conducting a DF/HCC Multi-Center protocol which includes but is not limited to:

- Oversee the coordination, development, submission, and approval of the protocol as well as subsequent amendments.
- Ensure that the investigators, study team members, and Participating Institutions are qualified and appropriately resourced to conduct the protocol.
- Include the Multi-Center Data and Safety Monitoring Plan as an appendix to the protocol.
- Ensure all Participating Institutions are using the correct version of the protocol.
- Ensure that each participating investigator and study team member receives adequate protocol training (and/or a Site Initiation Visit prior to enrolling participants) and throughout trial's conduct as needed.
- Ensure the protocol will be provided to each participating site.
- Monitor progress and overall conduct of the study at all Participating Institutions.
- Ensure all DFCI Institutional Review Board (IRB), DF/HCC, and other applicable reporting requirements are met.
- Review data and maintain timely submission of data for study analysis.
- Ensure compliance with all requirements as set forth in the Code of Federal Regulations, applicable DF/HCC requirements, HIPAA requirements, and the approved protocol.
- Commit to the provision that the protocol will not be rewritten or modified by anyone other than the DF/HCC Sponsor.
- Identify and qualify Participating Institutions and obtain accrual commitments prior to extending the protocol to that site.
- Monitor accrual and address Participating Institutions that are not meeting their accrual requirements.

**PROTOCOL TITLE: A New Paradigm of Transfusion Decision Support for Patients with MDS:
Using Peri-Transfusion Quality of Life Assessments (PTQAs)**

Coordinating Center

The general responsibilities of the Coordinating Center may include but are not limited to:

- Assist in protocol development.
- Review registration materials for eligibility and register participants from Participating Institutions in the DF/HCC clinical trial management system (CTMS).
- Distribute protocol and informed consent document updates to Participating Institutions as needed.
- Oversee the data collection process from Participating Institutions.
- Maintain documentation of Serious Adverse Event (SAE) reports and deviations/violation submitted by Participating Institutions and provide to the DF/HCC Sponsor for timely review and submission to the DFCI IRB, as necessary.
- Distribute serious adverse events reported to the DF/HCC Sponsor that fall under the DFCI IRB Adverse Event Reporting pPolicy to all Participating Institutions.
- Provide Participating Institutions with information regarding DF/HCC requirements that they will be expected to comply with.
- Carry out plan to monitor Participating Institutions either by on-site or remote monitoring.
- Maintain Regulatory documents of all Participating Institutions which includes but is not limited to the following: local IRB approvals/notifications from all Participating Institutions, confirmation of Federalwide Assurances (FWAs) for all sites, all SAE submissions, Screening Logs for all sites, IRB approved consents for all sites
- Conduct regular communications with all Participating Institutions (conference calls, emails, etc) and maintain documentation all relevant communications.

Participating Institution

Each Participating Institution is expected to comply with all applicable federal regulations and DF/HCC requirements, the protocol and HIPAA requirements.

The general responsibilities for each Participating Institution may include but are not limited to:

- Document the delegation of research specific activities to study personnel.
- Commit to the accrual of participants to the protocol.
- Submit protocol and/or amendments to their local IRB of record.
- Maintain regulatory files as per sponsor requirements.
- Provide the Coordinating Center with regulatory documents or source documents as requested.
- Participate in protocol training prior to enrolling participants and throughout the trial as required (i.e. teleconferences).
- Update Coordinating Center with research staff changes on a timely basis.
- Submit Serious Adverse Event (SAE) reports to local IRB per institutional requirements and to the Coordinating Center, in accordance with DF/HCC requirements.
- Submit protocol deviations and violations to local IRB per institutional requirements and to the DF/HCC Sponsor in accordance with DF/HCC requirements.
- Have office space, office equipment, and internet access that meet HIPAA standards.
- Participate in any quality assurance activities and meet with monitors or auditors at the

**PROTOCOL TITLE: A New Paradigm of Transfusion Decision Support for Patients with MDS:
Using Peri-Transfusion Quality of Life Assessments (PTQAs)**

conclusion of a visit to review findings.

- Promptly provide follow-up and/or corrective action plans for any monitoring queries or audit findings.

DF/HCC REQUIREMENTS FOR MULTI-CENTER PROTOCOLS

The following section will clarify DF/HCC Requirements and further detail the expectations for participating in a DF/HCC Multi-Center protocol.

Protocol Distribution

The Coordinating Center will distribute the final DFCI IRB approved protocol and any subsequent amended protocols to all Participating Institutions.

Protocol Revisions and Closures

The Participating Institutions will receive notification of protocol revisions and closures from the Coordinating Center. It is the individual Participating Institution's responsibility to notify its IRB of these revisions.

- **Non life-threatening revisions:** Participating Institutions will receive written notification of protocol revisions regarding non life-threatening events from the Coordinating Center. Non-life-threatening protocol revisions must be IRB approved and implemented within 90 days from receipt of the notification.
- **Revisions for life-threatening causes:** Participating Institutions will receive immediate notification from the Coordinating Center concerning protocol revisions required to protect lives with follow-up by fax, mail, e-mail, etc. Life-threatening protocol revisions will be implemented immediately followed by IRB request for approval.
- **Protocol closures and temporary holds:** Participating Institutions will receive notification of protocol closures and temporary holds from the Coordinating Center. Closures and holds will be effective immediately. In addition, the Coordinating Center, will update the Participating Institutions on an ongoing basis about protocol accrual data so that they will be aware of imminent protocol closures.

Informed Consent Requirements

The DF/HCC approved informed consent document will serve as a template for the informed consent for Participating Institutions. The Participating Institution consent form must follow the consent template as closely as possible and should adhere to specifications outlined in the DF/HCC Guidance Document on Model Consent Language for Investigator-Sponsored Multi-Center Trials. This document will be provided separately to each Participating Institution upon request.

Participating Institutions are to send their version of the informed consent document and HIPAA authorization, if a separate document, to the Coordinating Center for review and approval prior to submission to their local IRB. The approved consent form must also be submitted to the Coordinating Center after approval by the local IRB for all consent versions.

PROTOCOL TITLE: A New Paradigm of Transfusion Decision Support for Patients with MDS: Using Peri-Transfusion Quality of Life Assessments (PTQAs)

The Principal Investigator (PI) at each Participating Institution will identify the members of the study team (Research Assistant and Project Manager) who will be obtaining consent and signing the consent form. Participating institutions must follow the DF/HCC requirements for consent. As this study does not involve an investigational drug, biologic, or device, non-physicians (Research Assistants and Project Managers) are able to obtain consent and sign the consent forms.

IRB Documentation

The following must be on file with the Coordinating Center:

- Initial approval letter of the Participating Institution's IRB.
- Copy of the Informed Consent Form(s) approved by the Participating Institution's IRB.
- Participating Institution's IRB approval for all amendments.
- Annual approval letters by the Participating Institution's IRB.

IRB Re-Approval

Verification of IRB re-approval from the Participating Institutions is required in order to continue research activities. There is no grace period for continuing approvals.

The Coordinating Center will not register participants if a re-approval letter is not received from the Participating Institution on or before the anniversary of the previous approval date.

Participant Confidentiality and Authorization Statement

In 1996, congress passed the first federal law covering the privacy of health information known as the Health Insurance Portability and Accountability Act (HIPPA). Any information, related to the physical or mental health of an individual is called Protected Health Information (PHI). HIPAA outlines how and under what circumstances PHI can be used or disclosed.

In order for covered entities to use or disclose protected health information during the course of a study, the study participant must sign an authorization statement. This authorization statement may or may not be separate from the informed consent document. The Coordinating Center, with the approval from the DFCI IRB, will provide a consent template, with information regarding authorization for the disclosure of protected health information.

The DF/HCC Sponsor will use all efforts to limit its use of protected health information in its trials. However, because of the nature of these trials, certain protected health information must be collected. DF/HCC has chosen to use authorizations, signed by the participant in the trial, rather than limited data sets with data use agreements.

DF/HCC Multi-Center Protocol Confidentiality

All documents, investigative reports, or information relating to the participant are strictly confidential. Whenever reasonably feasible, any participant specific reports (i.e. Pathology Reports, MRI Reports, Operative Reports, etc.) submitted to the Coordinating Center should be de-identified. It is recommended that the assigned protocol case number (as described below) be used

**PROTOCOL TITLE: A New Paradigm of Transfusion Decision Support for Patients with MDS:
Using Peri-Transfusion Quality of Life Assessments (PTQAs)**

for all participant specific documents. Participant initials may be included or retained for cross verification of identification.

DF/HCC Multi-Center Protocol Registration Policy

Participant Registration and Randomization

Each site will be responsible for registering study participants according to their own institutional policies and procedures. The Coordinating Center will only register patients that are consented and enrolled at DFCI in the DF/HCC CTMS.

Although we will not register participants from Participating Institutions in the DF/HCC OnCore system, Participating Institutions will still be required to complete:

- Signed informed consent document
- Completed Eligibility Checklist

Participating Institutions will notify the Coordinating Center about registrations via monthly phone call.

Protocol-specific interventions may begin once the Participating Institution has registered the participant at their specific site.

Eligibility Exceptions

No exceptions to the eligibility requirements for a protocol without DFCI IRB approval will be permitted. All Participating Institutions are required to fully comply with this requirement.

DF/HCC Protocol Case Number

At the time of registration, the following identifiers are required for all subjects: initials, date of birth, gender, race and ethnicity. Once eligibility has been established and the participant successfully registered, the participant is assigned a unique protocol case number.

Case numbers will be assigned consecutively by DFCI as participants are enrolled. Participating Institutions will be responsible for tracking the appropriate case number as participants are enrolled.

Protocol Deviations, Exceptions and Violations

Federal Regulations require an IRB to review proposed changes in a research activity to ensure that researchers do not initiate changes in approved research without IRB review and approval, except when necessary to eliminate apparent immediate hazards to the participant. DF/HCC requires all departures from the defined procedures set forth in the IRB approved protocol to be reported to the DF/HCC Sponsor, who in turn is responsible for reporting to the DFCI IRB.

For reporting purposes, DF/HCC uses the terms “violation”, “deviation” and “exception” to describe departures from a protocol. All Participating Institutions must adhere to these requirements for reporting to the DF/HCC Sponsor and will follow their institutional policy for reporting to their local IRB.

**PROTOCOL TITLE: A New Paradigm of Transfusion Decision Support for Patients with MDS:
Using Peri-Transfusion Quality of Life Assessments (PTQAs)**

Definitions

Protocol Deviation: Any departure from the defined procedures set forth in the IRB-approved protocol which is *prospectively approved* prior to its implementation.

Protocol Exception: Any protocol deviation that relates to the eligibility criteria, e.g. enrollment of a participant who does not meet all inclusion/exclusion criteria.

Protocol Violation: Any protocol departure that was not *prospectively approved* by the IRB prior to its initiation or implementation.

Reporting Procedures

DF/HCC Sponsor: is responsible for ensuring that clear documentation is available in the medical record and/or regulatory documents to describe all protocol exceptions, deviations and violations. The DF/HCC Sponsor will also be responsible for ensuring that all protocol violations/deviations are promptly reported per DFCI IRB guidelines.

Participating Institutions: Protocol deviations require prospective approval from the DFCI IRB. The Participating Institution must submit the deviation request to the Coordinating Center who will then submit the deviation request to the DFCI IRB. Upon DFCI IRB approval the deviation is submitted to the Participating Institution IRB, per institutional policy. A copy of the Participating Institution's IRB report and determination will be forwarded to the Coordinating Center within 10 business days after the original submission. The deviation may not be implemented without all required approvals.

All protocol violations must be sent to the Coordinating Center in a timely manner. The Coordinating Center will provide training for the requirements for the reporting of violations.

Coordinating Center: Upon receipt of the violation/deviation report from the Participating Institution, the Coordinating Center will submit the report to the DF/HCC Sponsor for review. Subsequently, the Participating Institution's IRB violation/deviation report will be submitted to the DFCI IRB for review per DFCI IRB reporting guidelines. DF/HCC will forward all violation reports to CTEP via an internal DF/HCC process, as applicable.

Safety Assessments and Monitoring

The study teams at all participating institutions are responsible for protecting the safety, rights and well-being of study participants. Recording and reporting of adverse events that occur during the course of a study help ensure the continuing safety of study participants. As this is a survey study, we do not anticipate any issues with regards to patient safety.

Data Management

All sites, including the Coordinating Center and Participating Sites, will enter data into a RedCap database that will be managed by the study team. We will not use case report forms developed by DF/HCC CTRIO for this study.

**PROTOCOL TITLE: A New Paradigm of Transfusion Decision Support for Patients with MDS:
Using Peri-Transfusion Quality of Life Assessments (PTQAs)**

MONITORING: QUALITY CONTROL

The quality control process for a clinical trial requires verification of protocol compliance and data accuracy. The study team at the Coordinating Center will provide quality control oversight for the protocol.

Ongoing Monitoring of Protocol Compliance

The Coordinating Center will implement ongoing monitoring activities to ensure that Participating Institutions are complying with regulatory and protocol requirements, data quality, and participant safety. Monitoring practices may include but are not limited to source data verification, and review and analysis of eligibility requirements, informed consent procedures, adverse events and all associated documentation, review of study drug administration/treatment, regulatory files, protocol departures reporting, response assessments, and data management.

The Coordinating Center will monitor the progress of the study during monthly calls with Participating Institutions. During these call, the Coordinating Center will assess whether Participating Institutions are enrolling patients in a timely manner. In preparation for these calls, the Coordinating Center will prepare a data report to ensure timely completion of data entry tasks in RedCap.

Monitoring Reports

The DF/HCC Sponsor will review all monitoring reports to ensure protocol compliance. The DF/HCC Sponsor may increase the monitoring activities at Participating Institutions that are unable to comply with the protocol, DF/HCC Sponsor requirements or federal and local regulations.

Accrual Monitoring

Prior to extending a protocol to an external site, the DF/HCC Sponsor will establish accrual requirements for each participating institution. Accrual will be monitored for each participating institution by the DF/HCC Sponsor or designee. Sites that are not meeting their accrual expectations may be subject to termination. Each site will be expected to accrue 20 patients over the course of 18-months, with a minimum accrual requirement of 1-2 patients per month at each site.

AUDITING: QUALITY ASSURANCE

Auditing is a method of Quality Assurance and involves the systematic and independent examination of all trial related activities and documents. Audits determine if evaluated activities were appropriately conducted and whether data was generated, recorded and analyzed, and accurately reported per the protocol, applicable Policies, and the Code of Federal Regulations (CFR).

**PROTOCOL TITLE: A New Paradigm of Transfusion Decision Support for Patients with MDS:
Using Peri-Transfusion Quality of Life Assessments (PTQAs)**

DF/HCC Internal Audits

All Participating Institutions are subject to audit by the DF/HCC Office of Data Quality (ODQ). Typically, approximately 3-4 participants would be audited at the site over a 2-day period. If violations which impact participant safety or the integrity of the study are found, more participant records may be audited.

Audit Notifications

It is the Participating Institution's responsibility to notify the Coordinating Center of all external audits or inspections that involve this protocol. All institutions will forward a copy of final audit and/or re-audit reports and corrective action plans (if applicable) to the Coordinating Center, within 12 weeks after the audit date.

Audit Reports

The DF/HCC Sponsor will review all final audit reports and corrective action plans, if applicable. The Coordinating Center, must forward any reports to the DF/HCC ODQ per DF/HCC policy for review by the DF/HCC Audit Committee. For unacceptable audits, the DF/HCC Audit Committee would forward the final audit report and corrective action plan to the DFCI IRB as applicable.

Participating Institution Performance

The DF/HCC Sponsor and the IRB of record are charged with considering the totality of an institution's performance in considering institutional participation in the protocol.

Participating Institutions that fail to meet the performance goals of accrual, submission of timely and accurate data, adherence to protocol requirements, and compliance with state and federal regulations, may be recommended for a six-month probation period. Such institutions must respond with a corrective action plan and must demonstrate during the probation period that deficiencies have been corrected, as evidenced by the improved performance measures. Participating Institutions that fail to demonstrate significant improvement will be considered by the DF/HCC Sponsor for revocation of participation. A DF/HCC Sponsor and/or the DFCI IRB may terminate a site's participation if it is determined that a site is not fulfilling its responsibilities as described above.

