4.0 Study-Wide Number of Subjects

4.1 Accrual Goal

Our study-wide accrual goal is 60 evaluable participants. To reach this accrual goal, we will consent and enroll 90 participants as some participants are not able to complete the protocol due to a variety of reasons (e.g., participant does not end up requiring future transfusions). The 60 evaluable participants will be matched 1:1 to historical controls seen between 2015 and 2017, for a total sample size of 120.

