6.0 Multi-Site Research

6.1 Communication Plan

**PROTOCOL TITLE: A New Paradigm of Transfusion Decision Support for Patients with MDS:
Using Peri-Transfusion Quality of Life Assessments (PTQAs)**

As the lead site, DFCI will communicate study updates to participating sites (YCC and WFB) via phone call or email. For the duration of the study, the Research Project Manager (RPM) will ensure that all sites are using the most current version of the protocol and consent documents. YCC and WFB will be asked to send the DFCI study team all notifications of approval (including IRB approval of initial protocol, continuing reviews, and any study modifications). The DFCI study team will monitor the compliance of participating sites during monthly check-in phone calls. In the event of a study modification, potential modifications to the protocol will be discussed during monthly calls prior to implementation.

The DFCI study team will be responsible for all monitoring activities related to the study across all sites. We will implement a risk-based monitoring approach where monitoring activities will be at the discretion of the sponsor/PI ([name]).

We will monitor accrual during our monthly check-in calls. During these calls, we will ensure that all sites are enrolling between 1-2 patients per month. With regards to data monitoring, the DFCI RPM will review the RedCap database for missing/discrepant data every three months. The consent/eligibility for 10% of participants (2 at each site) will be verified with source documentation by the RPM. This will be done remotely and the participating sites will send the RPM the necessary source documentation.

6.2 As this study is minimal risk, we do not anticipate any problems or reportable events. All other problems, interim results, and study updates will be communicated via our monthly study phone call.

6.3 NA

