7.0 Study Timelines

7.1 Study Duration

- Individual subjects will participate in the study for approximately 10 weeks from the time of consent. This includes the completion of the pre-transfusion questionnaire, the post-transfusion questionnaire, and the follow-up survey at 8 weeks after transfusion. We will assess the number of hospitalizations and clinic visits for each participant 8 weeks after the index transfusion.
- We anticipate that it will take approximately 18 months to enroll 90 subjects across all three sites.
- The estimated date for the investigators to complete this study is April 30, 2020.

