20.2 Other Resources

The three study sites—DFCI, YCC, and WFB—all have large MDS populations and demonstrated track records in high-impact research in MDS, QOL, geriatrics and hematologic malignancies.

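### The site accrual expectation in Appendix H sums to 60, the evaluable goal, and is not reconciled with the 90 patients to be enrolled

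*Protocol*

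**What the plan says.** Section 4.1 separates two numbers. The goal is "Our study-wide accrual goal is 60 evaluable participants", and to get there "we will consent and enroll 90 participants as some participants are not able to complete the protocol". Section 11.1 repeats both. Section 7.1 gives the period: "We anticipate that it will take approximately 18 months to enroll 90 subjects across all three sites".

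Appendix H, under Accrual Monitoring, sets the requirement for sites: "Each site will be expected to accrue 20 patients over the course of 18-months, with a minimum accrual requirement of 1-2 patients per month". The same paragraph says that sites below expectation may be terminated. The later paragraph on institutional performance adds probation and revocation.

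Section 6.1 describes the monthly check: "we will ensure that all sites are enrolling between 1-2 patients per month". It also has consent and eligibility verified against source for one tenth of participants, which it puts at two per site.

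Two other places give counts. Section 23.2 speaks of approaching 90 patients to obtain 60 evaluable, and Section 23.1 makes the lead site's target depend on the external sites. The schema in Appendix F speaks of approaching 75 over 15 months, split 23, 23 and 29.

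**The concern.** The number against which sites are held to account should add up to the number the study needs to enrol. Here it adds up to the number it needs to have left after losses. The allowance for patients who consent but never become evaluable, one third of those enrolled, appears in Sections 4.1 and 11.1 and is absent from the monitoring plan.

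At stake is the sample of 30 per transfusion group on which Section 11.2 rests. If 20 means enrolled, every site could meet its expectation in full, no monitoring trigger would fire, and the study would still be 30 enrolled patients short.

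**Working it through.** **Inputs.** Three sites (Section 20.2); 20 per site over 18 months, with a floor of 1-2 per month (Appendix H); 90 enrolled for 60 evaluable (4.1); 18 months (7.1); 30 evaluable per transfusion group (9.1), matched 1:1 to controls (4.1). From 11.2: type I error 5%; 100% versus 70% in the naive group, stated power 85%; 8.0 versus 6.5 units with SD 2.0 in the dependent group, stated power 83%. Sidedness is not stated; two-sided reproduces both figures.

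**Counts.**
- Site expectation: 3 × 20 = 60, against 90.
- Monthly rate: 1-2 × 18 months = 18-36 per site, 54-108 in total.
- Needed for 90: 90/3 = 30 per site on average; 90/(3 × 18) = 1.67 per site per month.
- Source verification: 2 is 10% of 20, so 60 in total. Ten percent of 90 is 9, or 3 per site.
- Planned yield: 60/90 = 2/3. Applied to 60 enrolled: 60 × 2/3 = 40 evaluable, 20 per group if split evenly.

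**Plan's own power, n = 30 per arm.**
- Naive, pooled-variance normal approximation with continuity correction: power = Φ[(d − 1/n − 1.96·SE0)/SE1], with d = 0.30, SE0 = √(0.85 × 0.15 × 2/30) = 0.0922 and SE1 = √(0.21/30) = 0.0837. This is Φ[(0.30 − 0.0333 − 0.1807)/0.0837] = Φ(1.03) = 84.8%, matching the stated 85%. Fisher's exact test gives 92.3%.
- Dependent, normal formula: power = Φ[1.5/(2.0·√(2/n)) − 1.96] = Φ(2.905 − 1.96) = 82.8%, matching the stated 83%. A t-test gives 81.5%.

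**Same formulas, n = 20 per arm.**
- Naive: SE0 = √(0.85 × 0.15 × 2/20) = 0.1129 and SE1 = √(0.21/20) = 0.1025. Power = Φ[(0.30 − 0.05 − 0.2213)/0.1025] = Φ(0.28) = 61.0%. Fisher's exact test gives 76.2%.
- Dependent: Φ(2.372 − 1.96) = 66.0%. A t-test gives 63.7%.

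| Group | Method | n = 30 | n = 20 |
|---|---|---|---|
| Naive | normal, continuity-corrected | 84.8% | 61.0% |
| Naive | Fisher's exact | 92.3% | 76.2% |
| Dependent | normal | 82.8% | 66.0% |
| Dependent | t-test | 81.5% | 63.7% |

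**The case against.** The strongest reply is that Section 4.1 itself uses the term accrual goal for 60 evaluable participants. Three sites at 20 match that exactly, so Appendix H may simply share out the evaluable target, in which case nothing is lost. This reading cannot be excluded. Against it, Section 6.1 checks accrual by enrolment, Appendix H asks in the same part whether sites enrol in good time, and the verification of consent and eligibility, which concerns everyone enrolled, is also sized for 20 per site. The text is ambiguous, and a site cannot tell from it whether it owes 20 or 30 consents.

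Second, 20 is an expectation and not a cap. The monthly rate in the same sentence spans 54-108 in total, which includes 90, and nothing tells sites to stop. Section 23.1 lets the lead site act as the balancing item. This stands, with two limits: a floor stated as a range enforces only its lower end, and if 20 bound only the two external sites the lead site would need 90 − 40 = 50, or 50/18 = 2.8 per month, above the range in Section 6.1.

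Third, 40 evaluable is not a firm figure. The two-thirds yield is a planning allowance, here assumed equal in both groups. Section 11.4 treats patients without a pre-transfusion questionnaire as not enrolled, and would try to replace those without the post-transfusion one while still evaluating their outcomes. Section 11.1 is stricter and requires both questionnaires. The number analysed could therefore exceed 40.

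A reader might infer that the plan as written will end with 40 evaluable patients and power in the sixties. The documents do not support that: it needs the enrolled reading, every site stopping at 20, and the two-thirds yield in both groups.

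**Conclusion.** The mismatch is real: the site expectation sums to 60 while three sections plan 90 enrolled at the same three sites, two of them also tied to the same 18 months or the same loss allowance. It matters because the site figure carries sanctions and no allowance for non-evaluable patients.

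The power loss is a conditional worst case. On the enrolled reading, with sites stopping at 20 and a 60/90 yield in each group, about 20 per group remain. By the formulas that reproduce Section 11.2, power is then about 61% (naive) and 66% (dependent); across the other tests shown it runs from 61% to 76%. If 20 means evaluable, or if enrolment continues to 90, the stated 85% and 83% are unaffected. The point warrants a correction of the text. It does not show that the study is underpowered.

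**What to change.** 1. In Appendix H, either state the site targets as enrolled patients summing to 90 over 18 months (30 per site on average, with the lead site's share set as Section 23.1 allows; an equal split is not required), or label 20 as evaluable and give the enrolment target beside it.
2. In Section 6.1 and Appendix H, replace the 1-2 range with one monthly floor consistent with 90, about 1.7 per site per month on average, or 5 per site per three months.
3. In Section 6.1, align the verification count with 10% of 90, which is 9 in total.
4. In Section 23.2 and Appendix F, align the numbers to be approached. Approaching 75 cannot yield 90 enrolled, and approaching 90 does so only if all consent, although Aim 1 sets out to measure that proportion. The 15 months in Appendix F should be reconciled with the 18 in Section 7.1.

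The cost is a text amendment in four places. No patients beyond the planned 90 are needed.
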